**Table 15: Expected Power (YVD-CS01-EU and ZRHX-EX-01 Studies Assumptions)**

Assumptions	Reduction					
	50%	51%	52%	53%	54%	55%
YVD-CS01-EU	94%	88%	81%	70%	56%	38%
ZRHX-EX-01	98%	97%	92%	76%	41%	6%

A total of 160 smokers (80 in THS 2.2 Menthol, 40 in mCC, and 40 in the SA arms) were to be randomized over both sites. However due to the site that terminated due to ICH/GCP non-compliance 219 smokers were randomized, so that the 160 smokers would be recruited at the Tokyo Heart Center, to demonstrate a reduction of at least 50% on all 5 primary BoExp in smokers switching from mCC to THS 2.2 Menthol as compared to those continuing to smoke mCC, using one-sided test with 2.5% type I error probability. The calculation of the sample size was based on the assumption that 50% of the subjects in the THS 2.2 Menthol arm would be using THS 2.2 Menthol exclusively at Day 90.

9 CHANGES FROM THE PROTOCOL SPECIFIED STATISTICAL ANALYSIS

The term “adjusted to creatinine” has been replaced by “adjusted for creatinine” in all relevant endpoints and analyses.

The second exploratory objective (“To evaluate in smokers switching from mCC to THS 2.2 Menthol, and smokers continuing smoking mCC the relationship between NEQ and:

- Primary and secondary BoExp
- Selected risk markers and NEQ)

will be reported in a separate report.

Serology for human immunodeficiency virus (HIV) 1/2 cannot be transferred because of privacy laws, therefore this endpoint will not be presented in listings.

The PMI and [REDACTED] study statisticians will be unblinded after finalization of the SAP or database lock, whichever is later.

The PMI study scientist will be unblinded for the data review meeting, therefore the role of blinded reviewer is delegated.

Listing and summaries of spirometry predicted values will be presented standardized to the predicted set from the Japanese Respiratory Society, as measured by the spirometry devices.

10 ANALYSIS POPULATIONS

In pivotal pharmaceutical / therapy studies the general approach is to analyze the intention-to-treat (ITT) population. In such studies the product efficacy and the product compliance are generally highly correlated as the product effects may be detectable by the subject (e.g., relief from symptoms). Therefore, the ITT population is used to account for the effects of the product compliance. The drivers for product use (ultimately product compliance) for tobacco products are not the same as in a pharmaceutical setting. Smokers decide to smoke, despite the known risks and adverse health effects, based on social, cultural, personal, and psychological factors. Therefore the ITT approach may not be optimal in randomized studies evaluating modified risk tobacco products, as these products are targeting risk reduction which may not be the main factor influencing the choice of tobacco products used by the subjects.

The aim of this study is to demonstrate the optimal effect that could be achieved by the use of THS 2.2 in terms of reduction in BoExp. The following considerations were taken into account in order to measure “optimal effect” in this study:

1. The primary analysis is designed to assess the effect in subjects who are compliant with the assigned product use, rather than the effect in the full population. The full population would represent a heterogeneous exposure (e.g., as mixed product use, or non-use of the assigned product) rather than a THS 2.2 Menthol exposure.
2. The subjects are allowed to use the THS 2.2 Menthol product in a truly *ad libitum* setting (smoking is not restricted based on the number of CC smoked prior to study onset).

The optimal effect may be a somewhat ideal scenario, which differs from the real-world effect (effect under actual use setting) mainly by reducing the impact of non-compliance on the estimate. To be able to assess real-world effects we are planning to conduct studies, both in our clinical program (6 months exposure response studies) and in our perception and behavior program (actual use studies). In order to fully understand the full range of the potential effect THS 2.2 once it is commercialized it will be important to understand both the optimal effect and the real-world effect.

The PP Set will be the primary analysis for BoExp, and risk markers. The full analysis set will be the primary analysis set for compliance to randomization arm. Exposure and questionnaires will be described by randomization arm and according to product use categories (see Table 20).

A sensitivity analysis will be run on the compliant population for the for BoExp and risk markers.

Safety will be analyzed using the safety population and the full safety population by randomization arm and according to the product use categories (see Table 20).

10.1 Full Analysis Set

The FAS consists of all the randomized subjects who had at least one post-randomization product use experience, if randomized to THS 2.2 Menthol or mCC, and have at least one valid non-safety assessment (THS 2.2 Menthol, mCC, and SA arms). Subjects that were enrolled at the site that terminated due to ICH/GCP non-compliance will be excluded from the FAS.

10.2 Per Protocol Set

The PP set is a subset of the FAS and includes all randomized subjects who have no major protocol deviations impacting evaluability as defined in Table 16 (see section 11.1.1 “Major Protocol Deviations”).

The PP set is assessed for each product use time period 1 to 4 (see Table 20), considering the product deviations occurring only that period, independent of any exclusion from the population in previous periods.

10.3 Safety Populations

10.3.1 Safety Population

Before randomization, the safety population consists of all the subjects who had at least one exposure to THS 2.2 Menthol (including the product test at Admission Day). This also includes any randomized subjects who had no valid safety assessment post-randomization.

After the randomization, the safety population includes all randomized subjects who had at least one valid safety assessment post-randomization. Subjects in the safety populations will be analyzed according to product use categories defined over the whole ambulatory period.

Although subjects that were enrolled at the site that was terminated due to ICH/GCP non-compliance will be excluded from the safety population, they will be summarized within the Full Safety Population (see section 10.3.2 “Full Safety Population”).

10.3.2 Full Safety Population

The full safety population consists of all the subjects who had at least one exposure to THS 2.2 Menthol (including the product test at Admission Day). Safety evaluation will be presented before and after randomization as for the Safety population (see section 10.3.1 “Safety Population”)

10.4 Compliant Population

The compliant population will be a subset of the PP Set for subjects from the THS 2.2 Menthol arm who are exclusive THS 2.2 Menthol users, as defined in Section 10 “Analysis Populations”, or for subjects from the mCC arm who are exclusive users of

mCC, or for subjects in the SA arm who are abstinent, as defined in Section 6.3.3.2 “Abstinence from mCC use”.

11 PROTOCOL DEVIATIONS

Protocol deviations are defined as deviations from any procedure defined in the Study Protocol, including but not limited to, any violation of inclusion/exclusion criteria, mis-randomization, use of any nicotine or tobacco-containing product other than the assigned product during each of the exposure period in confinement, assessments not performed or performed outside the scheduled time windows, or use of drugs that are known to affect CYP2A6 activity.

Information following site monitoring and other reviews will be documented in the site visit reports, follow-up letters, audit documentation, or other manual review and subsequently recorded in an electronic data capture (EDC) system. Additional protocol deviations may be identified in the data review, these will also be recorded in the EDC system.

Additional protocol deviations (e.g. time windows for assessments) may be identified through programmatic checks and entered in ADaM datasets.

All deviations will be reviewed to determine their severity/impact when subjects are assigned to analysis populations. Each deviation will be classified as major or minor; all major deviations will be further reviewed to determine whether or not the deviation impacts the evaluability of the results and therefore should result in the subject being excluded from the PP Set.

11.1.1 Major Protocol Deviations

Subjects with major protocol deviations will be identified (per period of the study) to determine whether they will be excluded from any of the analysis populations. This will take place during the pre-analysis data review meeting prior to database lock. The categories for the major deviations will include, but are not limited to the deviations presented in Table 16.

**Table 16: Definition of Major Protocol Deviations**

Category	Description
Mis-randomization	Being administered the wrong product according to the randomization schedule.
Product compliance	Confinement: Use of any nicotine or tobacco-containing product other than the assigned product, using the product distribution log. Exhaled CO breath test >10 ppm for subjects from the SA arm starting from Day 2. Ambulatory: Non compliance in the THS 2.2 Menthol and SA arms will be defined for each period. Non compliance is based on product use reported in the product use Diary for Periods 2 - 4, as any of the following occurrence: - Use of more than 2 CC in a single day during the period. - Average product use from Day 1 through the end of the period is more than 0.5 CC per day.
Violation	Violation of inclusion/exclusion criteria.
Duration of 24 hour collection	Start and end times not within the 30 min window.

Among the violation of inclusion/exclusion criteria, only violations of inclusion criteria 1, 2, 4, 5 or of the exclusion criteria 2, 18 will be interpreted as impacting evaluability and lead to exclusion from the PP Set. Any violations of other inclusion or exclusion criteria will be assessed for their impact on the PP Set and evaluated during the pre-analysis data review meeting.

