6.5.4 Compliance to Investigational Product

During the confinement period, compliance for all study arms will be ensured by strict dispensation of the products (product by product) and collection of used Menthol Tobacco Sticks/CC butts will be documented in appropriate log..

During the ambulatory period, subjects in the 3 study arms will capture, from the time of Discharge on Day 6 to Day 90 11:00 PM the number of product used (e.g., menthol and non-menthol CC, Menthol Tobacco Sticks, or any other tobacco /nicotine-containing products including NRT) on a daily basis in the product use electronic diary. The product use electronic diary will be supplied by Sponsor and distributed to the subjects by the study site collaborator. The product use electronic diary will serve as a compliance tool in the three arms. On Day 6, the compliance to the product will be ensured by the merge of the

accountability log (from 06:30 AM to time of discharge) and the product use electronic diary. In case of discrepancy between the log and the electronic diary entries, the electronic diary entries will be considered as source of data.

In addition, in the SA arm, compliance will be chemically verified using an exhaled CO breath test during both the confinement and ambulatory periods. The cut-off point for the CO breath test value to distinguish mCC use versus no mCC use will be 10 ppm (Benowitz et al., 2002).

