6.3.3 Compliance to Product Allocation

During the confinement period, compliance to product/regimen allocation (exclusive use of THS 2.2 Menthol and mCC in THS 2.2 Menthol and mCC arms, respectively, and full abstinence from smoking in the SA arm) will be ensured by strict distribution of each Tobacco Stick/mCC when requested by the subject. During the ambulatory period, the subjects randomized to the THS 2.2 Menthol arm will be instructed to exclusively use THS 2.2 Menthol and subjects randomized to the SA arm will be instructed to abstain from smoking.

In addition, in subjects in the SA arm, the compliance will be chemically verified in confinement using exhaled CO breath. The cut-off point for the CO breath test value to distinguish CC use vs. no CC use will be 10 ppm (Benowitz et al. 2002). No subjects

from the SA arm will be withdrawn from the study if their exhaled CO breath test results are >10 ppm.

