6.3.3.2 Abstinence from mCC use

In order to further optimize the assessment of BoExp and increase the comparability of the levels of BoExp between THS 2.2 Menthol and SA the confounding effects of the use of any other tobacco or nicotine containing product (other than the assigned product) needs to be controlled for. Therefore a subject will be considered abstinent based on the following categorization:

- “Abstinence”: full abstinence from tobacco or nicotine containing product use other than the assigned product, biochemically verified with CO breath test ≤ 10 ppm.
- “Predominantly abstinent”: not more than 0.5 uses of any tobacco or nicotine containing product (other than the assigned product) per day on average and no more than two uses on a single day.
- “Not abstinent”: more than 0.5 uses of any tobacco or nicotine containing product (other than the assigned product) per day on average or more than two uses on a single day.

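### The SAP does not carry the protocol's ambulatory exhaled-CO check of the abstinence arm into the Per-Protocol rule for Periods 2 to 4, and does not declare the change

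*SAP*

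**What the plan says.** **Protocol.** Section 6.5.4 makes the electronic diary a compliance tool in all three arms and adds that "in the SA arm, compliance will be chemically verified using an exhaled CO breath test during both the confinement and ambulatory periods". The cut-off is 10 ppm. Section 7.5.1.1 repeats that CO verifies SA compliance and schedules one breath test at each of the Day 30, 60 and 90 Visits.

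**SAP, restricting CO to confinement.** Section 6.3.3 states that "the compliance will be chemically verified in confinement using exhaled CO breath". Table 16 lists, under confinement only, "Exhaled CO breath test >10 ppm for subjects from the SA arm starting from Day 2". For the ambulatory phase it says "Non compliance in the THS 2.2 Menthol and SA arms will be defined for each period", and then "Non compliance is based on product use reported in the product use Diary for Periods 2 - 4". The criteria are more than 2 cigarettes on one day or an average above 0.5 per day. The only CO-compliance output, Table 15.2.5.1, covers confinement. Section 9, on changes from the protocol, does not mention this.

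**SAP, using CO without a period limit.** Section 12.4 makes CO a compliance tool in the SA arm from Day 2 and gives no end date. Section 6.3.3.2 requires CO of 10 ppm or less for the *Abstinence* category. It sets no CO condition for *Predominantly abstinent*, defined as "not more than 0.5 uses of any tobacco or nicotine containing product (other than the assigned product) per day on average" with at most two uses on any day.

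**The concern.** SA is the protocol's reference point for the maximum possible reduction in exposure (Section 4.2). The PP Set is the primary population for biomarkers of exposure (BoExp) and risk markers. THS versus SA is modelled on it for BoExp (SAP 12.6.2 and 12.6.2.1), CYP1A2 (12.6.2.4) and risk markers (12.6.2.5).

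The PP rule keeps the objective check while cigarettes are handed out one at a time. It relies on self-report for the 85 ambulatory days, when protocol 4.2 itself anticipates some cigarette smoking. If some SA subjects smoke without recording it, the PP reference group is less abstinent than its label says, and the THS:SA ratio for BoExp is pulled down. The readings that could expose part of this are already collected but have no written role in ambulatory PP membership.

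**Working it through.** **1. Trace one subject through the rules.** Take an SA subject whose Period 4 diary shows no cigarettes and whose Day 90 breath test reads 25 ppm (a hypothetical value).

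- Table 16, ambulatory: neither diary criterion is met, and the CO criterion sits under confinement. No written exclusion applies.
- Missing-diary rule (SAP 12.1.5): this counts missing days as baseline smoking when fewer than 75% of entries are present or a gap exceeds 7 days. It catches absent entries, not false zeros.
- Section 6.3.3.2: the subject fails *Abstinence* on CO, meets *Predominantly abstinent* on use counts, and does not meet *Not abstinent*.

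Under the written rules the subject stays in the Period 4 PP Set.

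**2. Possible size.** The plan states no figure for this effect, so there is none to reproduce. The inputs are the Day 5 mean ratios in protocol Table 19 (SAP Table 11). They are read on the log scale. With SD = √ln(1+CV²), a null ratio of 0.50, one-sided 2.5%, 80:40 subjects (40:40 for Total NNAL) and the product over five endpoints, that reading gives power of 94.3% and 98.2%. The 50% column of protocol Table 23 has 94% and 98%. Several columns further right fit less well; they are not used here.

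The documents give no misreporting rate. Let c be the assumed share of SA subjects with full mCC-level exposure. Then:

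- mCC/SA = (THS/SA) ÷ (THS/mCC)
- observed THS:SA = (THS/SA) × (mCC/SA)^(−c)

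For COHb, mCC/SA = 2.10/0.40 = 5.25, and at c = 10% the ratio is 2.10 × 5.25^(−0.1) = 1.78.

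| Marker | THS/mCC | THS/SA | mCC/SA | c = 5% | c = 10% | c = 20% | c = 30% |
|---|---|---|---|---|---|---|---|
| COHb | 0.40 | 2.10 | 5.25 | 1.93 | 1.78 | 1.51 | 1.28 |
| 3-HPMA | 0.30 | 1.70 | 5.67 | 1.56 | 1.43 | 1.20 | 1.01 |
| S-PMA | 0.20 | 1.15 | 5.75 | 1.05 | 0.97 | 0.81 | 0.68 |
| MHBMA | 0.15 | 1.00 | 6.67 | 0.91 | 0.83 | 0.68 | 0.57 |

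The falls are 8 to 9% at c = 5%, 15 to 17% at 10% and 28 to 32% at 20%. If the unreported smokers have half the mCC exposure, c = 10% gives 1.91, 1.53, 1.03 and 0.89 in table order.

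**3. Direction.** Unreported smoking in the THS arm multiplies THS:SA by (THS/mCC)^(−c).

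| 10% unreported smoking in | COHb | 3-HPMA | S-PMA | MHBMA |
|---|---|---|---|---|
| SA only | 1.78 | 1.43 | 0.97 | 0.83 |
| Both arms | 1.95 | 1.61 | 1.13 | 1.00 |
| THS only | 2.30 | 1.92 | 1.35 | 1.21 |

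The sign of the net bias therefore depends on which arm misreports more.

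**The case against.** Several stronger readings are tempting, and the documents do not support them.

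- **That CO verification is abandoned after confinement.** It survives in SAP 12.4, in the *Abstinence* category and, through that category, in the Compliant Population (SAP 10.4). Exhaled CO and COHb are also summarised over time. The SAP is inconsistent within itself. However, 10.4 does not say which 6.3.3.2 category counts as abstinent.
- **That every Day 90 THS versus SA comparison is affected through this rule.** The FAS comparisons are not governed by Table 16, and Table 15.2.3.7 compares the additional BoExp with SA in the Compliant Population. This stands, with two limits. The FAS keeps the same subjects, so it is not a CO-verified alternative. For the five primary BoExp, SAP 12.6.1.3 specifies the Compliant Population model for THS versus mCC only, and the listed CYP1A2 and risk-marker analyses use only the PP Set and FAS. The revision history mentions a compliant-population comparison with SA, so adding one would fit the stated intention.
- **That the rule flatters THS.** That assumes misreporting in SA only. The THS arm has the same diary-only rule, and step 3 shows the opposite sign is possible. Cleaning SA alone also leaves any THS misreporters in place.
- **That Table 16 contradicts the protocol's PP definition.** Protocol 12.4.2 counts cigarettes only, and 12.1.2 defines abstinence from the diary. The conflict is with 6.5.4 and 7.5.1.1.

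Two further points have force. SAP 11.1.1 leaves the list open: "The categories for the major deviations will include, but are not limited to the deviations presented in Table 16". A high CO reading could therefore be adjudicated at data review, but nothing requires it, and SAP 6.3.2 has the study scientist unblinded for that meeting. Also, one breath test per visit detects mainly recent smoking. Protocol 4.2 puts the half-life of the Day 5 markers, COHb included, at 24 hours or less.

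**Conclusion.** The inconsistency is established from the text. Protocol 6.5.4 promises an ambulatory CO check in the SA arm, the SAP's PP rule omits it, Section 9 does not say so, and other parts of the SAP still assume CO is used. The consequence is limited to PP-based THS versus SA comparisons in the ambulatory period. For BoExp, unreported smoking in SA alone lowers THS:SA; the net direction is not determined by the documents.

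The size is unknown. The 15 to 17% figure assumes that 10% of PP SA subjects have full mCC exposure and that Day 5 confinement ratios apply at Day 90. It does not cover Total NNAL, CYP1A2 or risk markers, for which Table 19 gives no THS/SA ratio. The confirmatory test and success criterion compare THS with mCC and are unaffected.

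**What to change.** Preferred: reconcile SAP 6.3.3, 6.3.3.2 and Table 16 with protocol 6.5.4.

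- In Table 16 (ambulatory), treat exhaled CO above 10 ppm in an SA subject at the Day 30, 60 or 90 Visit as non-compliance for Period 2, 3 or 4 respectively.
- In 6.3.3.2, class such a subject as *Not abstinent* for that period, whatever the diary shows.
- Extend 6.3.3 and Table 15.2.5.1 to the ambulatory visits.

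This concerns analysis-set membership only, not withdrawal from the study.

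Alternative: keep the diary rule, declare the departure in Section 9, and add THS versus SA sensitivity analyses restricted to CO-verified SA subjects for the five primary BoExp, CYP1A2 and risk markers.

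The cost is SAP wording and programming, since the readings are already collected. Under the preferred route a few SA subjects would leave the ambulatory PP Set, some possibly because of environmental CO. A single reading per visit will still miss smoking that is not recent.

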11.1.2 Minor Protocol Deviations

The categories for the minor deviations will include, but are not limited to the deviations presented in Table 17.

Table 17: Definition of Minor Protocol Deviation Categories

Category	Description
Concomitant medication	Use of drugs which are known to affect 11-DTX-B2, CYP2A6 or CYP1A2 activity.
Procedural violation	Violation of planned procedure
Time deviation (Questionnaires)	Assessments not taken at the correct time or within the allowed time window (see Table 18)

**Table 17: Definition of Minor Protocol Deviation Categories**

Category	Description
Time deviation (Blood draws)	Assessments not taken at the correct time or within the allowed time window (see Table 18)
Time deviation (CYP1A2 activity)	Assessments not taken at the correct time or within the allowed time window (see Table 18)
Time deviation (CYP2A6 activity)	Assessments not taken at the correct time or within the allowed time window (see Table 18)
Time deviation (Assessment of cough)	Assessments not taken at the correct time or within the allowed time window (see Table 18)
Time deviation (CO breath test)	Assessments not taken at the correct time or within the allowed time window (see Table 18)
Time deviation (HST Recording)	Assessments not taken at the correct time or within the allowed time window (see Table 18)
Visit window deviation	Day 30, Day 60 and Day 90 Visits outside of visit window (see Table 18).
Time missing	Assessment date or time is missing
Assessment missing	Assessment is missing
Visit missing	Scheduled visit not done

11.1.3 Assessment Windows

During the confinement period, smoking of the randomized products should take place within the 06:30 AM and 11:00 PM window.

The assessment windows are shown in Table 18.

Table 18: Assessment Windows

Assessment	Nominal Time point(s)	Window
24 h urine sample	Start (Days -1 to 5) Start (Days 30, 60 and 90) End (Days 0 to 6) End (Days 31, 61 and 91)	06:30 AM \pm 20 min 09:00 AM \pm 20 min 06:29 AM \pm 20 min 08:59 AM \pm 20 min
CYP1A2 activity in plasma	Day 0, Day 5 and Day 90	6 h \pm 15 min after intake of caffeine tablet

Assessment	Nominal Time point(s)	Window
CYP2A6 activity	Day 0, Day 6 and Day 91	Prior to smoking / product use
CO breath test	Day -2 Morning (Days -1 to 5) Day -1 to Day 5 Day 6 Day 30 and Day 60 Day 90	Time of admission to 06:30 PM irrespective of product use To be done within 15 minutes prior to smoking/product use (for THS 2.2 Menthol and mCC arms) or between 08:00 AM and 09:30 AM (SA arm) Between 12:00 PM and 01:30 PM, 04:00 PM and 05:30 PM, and 08:00 PM and 09:30 PM Prior to discharge Between 10:00 AM and 11:30 AM. Irrespective of product use Between 10:00 AM and 12:30 AM. Irrespective of product use
Assessment of Cough	Days 0 to 6 Day 31 and Day 61 Day 91	To be done prior to product use but not later than 10:00 AM. Irrespective of product use but no later than 10:00 AM Prior to smoking but no later than 10:00 AM
MNWS questionnaire	Day 0 to 6 Day 31 and Day 61 Day 91	To be done prior to product use but not later than 10:00 AM Irrespective of product use but no later than 10:00 AM To be done prior to product use but not later than 10:00 AM
QSU-brief questionnaire	Days -1 to 5, Days 30, 60 and 90	08:00 PM to 11:00 PM
mCEQ questionnaire	Days -1 to 5, Days 30, 60 and 90 Days 0 to 4	08:00 PM to 11:00 PM 08:00 PM to 09:30 PM

Assessment	Nominal Time point(s)	Window
Nicotine and cotinine in plasma	Day 5 for THS 2.2 Menthol and mCC arms: within 15 minutes before first product use (T0): then additional blood samples at 2 hour intervals from T0 until 11:00 PM. In SA arm only one blood sample between 08:00 PM to 09:30 PM	Each sample has a 5 minute time window
	Day 6 for THS 2.2 Menthol and mCC arms: 20 and 24 h after T0 of Day 5. In SA arm only one blood sample between 08:00 AM to 09:30 AM.	5 minute time window
COHb blood sampling	Days -1 to 4 Morning sample on Day 5 Day 5 other samples Day 30 and Day 60 Day 90	08:00 PM to 09:30 PM Within 15 minutes prior to product use (for THS 2.2 Menthol and mCC arms) or between 08:00 AM and 09:30 AM (SA arm) Between 12:00 PM and 01:30 PM, 04:00 PM and 05:30 PM, and 08:00 PM and 09:30 PM Irrespective of product use between 10:00 AM and 11:30 AM. Irrespective of product use between 10:00 AM and 12:30 AM.
HST Questionnaire	Day 0 Day 4, Day 30, Day 60 and Day 90 for all subjects in the THS 2.2 Menthol and mCC arms	08:00 PM-11:00 PM 08:00 PM-09:30 PM
HST Recording	Day 0 Day 1 and Day 4 for all subjects in the THS 2.2 Menthol and mCC arms smoking compatible mCC Day 30, Day 60 and Day 90 for all subjects in the THS 2.2 Menthol and mCC arms smoking compatible mCC	06:30 AM-11:00 PM 06:30 AM-11:00 PM Start time: 08:30 AM to 09:30 AM. End time: 12:30 PM to 01:30 PM. 4-hour recordings ± 15 min
Ambulatory Visit	Day 30 Visit, Day 60 Visit and Day 90 Visit	± 3 days.

